## 6.2 Chronic Graft versus Host Disease (GVHD)

For patients who initiate therapy and develop new onset chronic GVHD:

- Therapy with topical / local agents such as corticosteroid / tacrolimus cream, oral non-absorbable steroids, ursodiol, etc. are allowed to be used and ivosidenib will continue. Discussion with the Principal Investigator is encouraged.
- Systemic therapy  $\leq 1$  mg/kg/day of prednisone is allowed to be used with continuation of ivosidenib. In no way is this study advocating for the use of a specific dose of steroids for initial therapy of chronic GVHD, and treatment of such should not be compromised to continue ivosidenib.
- If requiring systemic steroids  $> 1$  mg/kg/day of prednisone, ivosidenib will be held and initial therapy for chronic GVHD initiated. If within the next 28 days, the participant is able to improve and be on a stable dose of steroids which is  $\leq 1$  mg/kg/day of prednisone (or equivalent), ivosidenib may be restarted at the original dose.

---

CONFIDENTIAL

This document is confidential. Do not disclose or use except as authorized.

- Participants are forbidden from receiving any “investigational” agents for the treatment of chronic GVHD. Discussion with the overall PI is encouraged to defined “investigational.” Participants are allowed to participate on clinical trials investigating initial therapy for chronic GVHD – i.e. using agents with steroids or agents alone which are not “investigational.”
- Any initiation of systemic therapy beyond steroids for steroid-refractory chronic GVHD will result in the patient stopping ivosidenib. Systemic therapy beyond steroids for participants with *steroid-dependent* chronic GVHD is allowed and will not result in participant stopping ivosidenib. Discussion with the PI is encouraged.
- For flares of chronic GVHD, participants are allowed to increase systemic steroid dose, however, if exceeding 1 mg/kg/day of prednisone or equivalent, ivosidenib will be held and the patient will have 28 days to restart if symptoms and steroid requirement guidelines can be met.

### **6.3 Non-Hematologic Toxicity (except QT prolongation)**

If at any time during ivosidenib dosing, a participant experiences a grade 3 or higher toxicity that is possibly, probably or definitely related to ivosidenib, drug must be held until the toxicity resolves to a grade 1 or lower. If it is during the first cycle (28 days) of dosing, the toxicity will be considered to be a DLT (see section 5.4). In participants with known Gilbert’s disease, grade 3 elevated bilirubin that is possibly, probably or definitely related to ivosidenib would not require study drug hold if the elevation is not due to liver GVHD or veno-occlusive disease. For these participants, study drug must be held for grade 4 elevated bilirubin and resolution/recurrence of toxicity to follow the instructions below in 6.3.1 and 6.3.2.

If and when ivosidenib is held in the midst of a cycle, the cycle day will not change, and once the drug is resumed it will be either on the day that that cycle has progressed to, or if the pause is beyond 28 days of a cycle, the resumption will be called the day 1 of the subsequent cycle.

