#### **5.4 Definition of Dose-Limiting Toxicity (DLT)**

Dose-limiting toxicities will be evaluated during cycle 1 (first 28 days) of treatment. Toxicities will be graded and documented according to NCI CTCAE version 4.03.

Non-hematologic DLTs will be defined as any drug-related grade 3 or greater event.

The following exceptions will NOT be considered DLTs in this population:

- grade 3 nausea, vomiting, or diarrhea that lasts  $\leq$  72 hours and responds to medical intervention

Hematologic DLTs will be defined as any drug-related grade 4 neutropenia ( $ANC < 500/\mu L$ ) or thrombocytopenia (platelets  $< 25,000/\mu L$ ) that

- has not resolved to grade 1 or less within 14 days of holding ivosidenib, or
- resolves within 14 days, but then recurs after resuming study drug

Note that anemia is not included as a DLT.

Additionally, febrile neutropenia of any duration, and not due or attributable to the underlying disease or other extraneous causes such as infection, will be considered a DLT.

In addition, any  $\geq$  grade 2 non-hematologic toxicity that the participant finds intolerable or renders the participant unable to take 75% of the assigned doses (e.g. multiple dose interruptions) during the first cycle will be considered a DLT.

Management and dose modifications associated with the above events are outlined in Section 6.

Dosing will proceed within each cohort according to the following scheme.

Number of observed DLTs at a Given Dose Level	Decision Rule
0/3	3 additional evaluable patients will be treated at the dose level. If $\leq 1$ of the 6 treated patients experience a DLT, this is the RP2D. If $\geq 2$ of the 6 treated patients experience a DLT and current dose is dose level 2, de-escalate to dose level 1.
$\geq 2$	De-escalate to dose level 1 if current dose is dose level 2.

CONFIDENTIAL

This document is confidential. Do not disclose or use except as authorized.

1/3	Add 3 more patients at current dose level  a) If 0 of these 3 additional patients experience DLT, current dose is RP2D.  b) If $\geq 1$ of these 3 additional patients experience DLT, then de-escalate to dose level 1 if current dose is dose level 2.
$\leq 1/6$	Current dose is the RP2D

Subsequent (after cycle 1) cycles of ivosidenib will continue, with participants monitored for toxicity and adverse event reporting, but will not be used for DLT evaluation.

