#### **6.3.1 250 mg dosing**

If the participant was at the 250mg daily dosing level when the toxicity occurred, and it takes longer than 14 days for the event to resolve to  $\leq$  grade 1, then the participant will be taken off treatment and will remain on study only for survival and other outcomes.

If the toxicity takes less than 14 days to resolve to  $\leq$  grade 1, then ivosidenib can be restarted at 250mg daily dosing upon resolution. If the attributable toxicity recurs at  $\geq$  grade 3 (or grade 4 bilirubinemia in those with known Gilbert’s disease – see above section 6.3) during the course of the study, then the participant will come off treatment and will remain on study only for survival and other outcomes. If the toxicity recurrence (to  $\geq$  grade 3) happens during the first cycle of dosing, then the event will be a DLT.

---

CONFIDENTIAL

This document is confidential. Do not disclose or use except as authorized.

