### 6.3.2 500 mg dosing

If the participant was at the 500mg daily dosing level when the toxicity occurred, and the toxicity resolves to  $\leq$  grade 1 *after* 14 days, but *before* 28 days (total) have elapsed, then dosing with ivosidenib can resume at the reduced dose of 250 mg daily. If the attributable toxicity recurs at  $\geq$  grade 3 (or grade 4 bilirubinemia in those with known Gilbert's disease – see above section 6.3) during the course of the study, then the participant will come off treatment and will remain on study only for survival and other outcomes.

If the participant was at the 500mg daily dosing level when the toxicity occurred, and it takes *less than* 14 days for the event to resolve to  $\leq$  grade 1, then dosing with ivosidenib can resume at 500mg daily. If the toxicity recurs at  $\geq$  grade 3 (or grade 4 bilirubinemia in those with known Gilbert's disease – see above section 6.3), then dosing will again be held. (This will be a DLT if it occurs during cycle 1). If the toxicity again resolves to  $\leq$  grade 1 within 28 days, then dosing with ivosidenib can resume at the reduced dose of 250mg daily. If the toxicity recurs yet again at  $\geq$  grade 3 (or grade 4 bilirubinemia in those with known Gilbert's disease – see above section 6.3), then the participant will come off treatment and will remain on study only for survival and other outcomes.

A participant who starts at 500mg daily dosing and is subsequently reduced to 250mg daily dosing due to toxicity can potentially increase back up to 500mg daily dosing if subsequent evaluation of the observed toxicity indicates no relation to study drug. Any such re-escalation must have the approval of the principal investigator, [name].

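### Section 6.3 counts every related grade 3 or higher non-hematologic toxicity in cycle 1 as a DLT, while Section 5.4 exempts short, treatable gastrointestinal events, so the same event can be scored either way

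*Combined protocol and SAP*

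**What the plan says.** Section 5.4, which carries the DLT definition, states: "Non-hematologic DLTs will be defined as any drug-related grade 3 or greater event". It then introduces an exclusion: "The following exceptions will NOT be considered DLTs in this population". The only item listed is grade 3 nausea, vomiting or diarrhea, limited to events lasting no longer than "72 hours and responds to medical intervention". For non-hematologic events, Section 5.4 sets no recurrence condition and has no rule for Gilbert's disease. It refers the reader to Section 6 for management and dose modification.

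Section 6.3 covers "a grade 3 or higher toxicity that is possibly, probably or definitely related to ivosidenib, drug must be held until the toxicity resolves" to grade 1 or lower. Its next sentence reads: "If it is during the first cycle (28 days) of dosing, the toxicity will be considered to be a DLT (see section 5.4"). It then turns to known Gilbert's disease, where a grade 3 bilirubin elevation "would not require study drug hold if the elevation is not due to liver GVHD or veno-occlusive disease".

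Sections 6.3.1 and 6.3.2 add DLT statements about recurrence. At 250 mg, a recurrence to grade 3 or higher that "happens during the first cycle of dosing, then the event will be a DLT". At 500 mg, the sentence on recurrence gives grade 3 or higher, or grade 4 bilirubin in known Gilbert's disease, and is followed by "This will be a DLT if it occurs during cycle 1".

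Section 13 refers DLT assessment to the definition in Section 5. Under the decision table, at most 1 of 6 participants with a DLT makes the dose the RP2D. Two or more lead to de-escalation from 500 mg, or to discontinuation of the trial at 250 mg.

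**The concern.** The DLT count is the only input to the RP2D decision, which is the primary endpoint. With three or six evaluable participants per dose level, each classification carries weight. If the section used to manage toxicity words the rule differently from the section that defines it, two investigators in this multi-center trial could record the same cycle 1 event differently, each with text to support the entry. The gastrointestinal difference pushes the DLT count up if Section 6.3 is applied as written. The 6.3.2 threshold could push it down for bilirubin in Gilbert's disease.

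**Working it through.** **Design figures.** The sample size range of 6-22 reproduces: the minimum is 3 + 3 = 6 (both doses fail in their first three participants) and the maximum is 6 + 6 + 10 = 22. The stated 90% precision of ±22% with 16 participants also reproduces: the exact (Clopper-Pearson) interval at 8/16 runs from 27.9% to 72.1%, a half-width of 22.1%. Neither figure depends on which DLT wording applies.

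**Side by side, gastrointestinal event.** Take a drug-related grade 3 diarrhea in cycle 1 that settles in 48 hours on treatment. Suppose that the participant does not find it intolerable and can take at least 75% of doses (0.75 × 28 = 21), so that the separate tolerability clause of Section 5.4 is not met.
- Section 5.4: grade 3 and related, but within the exclusion. Not a DLT.
- Section 6.3: grade 3, related, in cycle 1. A DLT.

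This is a direct contradiction.

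**Side by side, bilirubin in known Gilbert's disease.**
- Section 5.4: a related grade 3 event is a DLT, with no exception for bilirubin.
- Section 6.3: the DLT sentence is unqualified; the Gilbert's text that follows concerns holding the drug only.
- Section 6.3.1: the DLT sentence gives grade 3 or higher, unqualified.
- Section 6.3.2: the DLT statement follows a sentence that uses grade 4 for these participants.

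Only the last entry is out of line.

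**Side by side, recurrence.** A first non-exempt grade 3 event is already a DLT under Sections 5.4 and 6.3. The table counts participants with a DLT, so a second event in the same participant adds nothing.

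**Effect on the decision.** The 3+3 table passes a dose when at most 1 of 6 has a DLT. With per-participant DLT probability p:

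P(pass) = (1 − p)^6 + 6p(1 − p)^5

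At p = 0.10: 0.5314 + 0.3543 = 0.886.

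The documents state neither a DLT rate nor a rate of discordant events, so both are assumed. Let d be the extra proportion of participants counted under Section 6.3 but not Section 5.4, added to p:

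| DLT rate under 5.4 | d = 0 | d = 2% | d = 5% | d = 10% |
|---|---|---|---|---|
| 10% | 88.6% | 84.4% | 77.6% | 65.5% |
| 20% | 65.5% | 60.6% | 53.4% | 42.0% |

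If the discordant events are instead independent of other DLTs, p becomes 1 − (1 − p)(1 − d). The 10% row is then 84.9%, 78.8% and 68.0%, which is little different.

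The chance of at least one discordant participant among six is 1 − (1 − d)^6 = 11.4%, 26.5% or 46.9% for d = 2%, 5% or 10%.

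**How often one discordant participant is decisive.** The result flips only if exactly one of the other five has a DLT. At p = 0.10 this is 5 × 0.10 × 0.90^4 = 0.328, about one time in three.

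**The case against.** The best defense is that the documents indicate which section governs. Section 13 sends the reader to Section 5 for the definition, Section 5.4 gives Section 6 a management role, and the disputed sentence itself points to Section 5.4. On that reading Section 6.3 is an incomplete paraphrase. This stands as the likely intent, and it rules out the inference that the trial has two rival endpoint definitions of equal standing. It does not remove the contradiction: the Section 6.3 sentence has no condition, and no text says expressly that Section 5.4 prevails where the two differ.

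Four stronger readings are tempting and are not supported:
- **The recurrence sentences mean that a first event does not count.** They do not say so, and Section 6.3 says the opposite. They resemble the hematologic text in Sections 6.7.1 and 6.7.2, where recurrence is a real criterion under Section 5.4. Here they are mainly redundant, though open to misreading.
- **The Gilbert's text in Section 6.3 is itself a DLT rule, or a DLT without a drug hold is contradictory.** That text concerns the hold and is silent on scoring. Classifying an event for the cohort and dosing an individual are separate matters.
- **One reclassified event always changes the dose decision.** Both 0/6 and 1/6 pass, so it is decisive only at the boundary.
- **The any-grade rates in Section 2.3 (diarrhea 30%, nausea 26%) support a particular discordance rate.** They are not restricted to grade 3, related, cycle 1 or short events, and they come from advanced disease rather than remission after transplant.

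Nor do the documents show that sites will score from Section 6 while the analysis uses Section 5.4; that is conjecture.

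**Conclusion.** The point holds in two places. Section 6.3 contradicts Section 5.4 on short, treatable grade 3 gastrointestinal events, and the grade 4 threshold beside the DLT statement in Section 6.3.2 is in tension with Section 5.4 and Section 6.3.1. The recurrence sentences are a lesser matter of clarity.

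One discordant event can turn 1/6 into 2/6. How often that would happen cannot be derived from the documents. The pass probabilities above rest on assumed rates and on every discordant event being scored under Section 6.3 despite its cross-reference, so they are illustrations rather than forecasts. The case for a change rests on the contradiction in the primary endpoint's definition. The sponsor should correct it, but it does not undermine the design.

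**What to change.** Keep one DLT definition, in Section 5.4. In Sections 6.3, 6.3.1 and 6.3.2, replace each sentence that declares an event or recurrence a DLT with an instruction to assess it against Section 5.4. The sponsor should reconcile how bilirubin elevation in known Gilbert's disease is classified, so that all of these sections give the same answer. No clinical threshold is proposed here.

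The cost is a wording amendment. Sample size, data collection, the decision table and the precision statement are unchanged.

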#### **6.3.1 250 mg dosing**

If the participant was at the 250mg daily dosing level when the toxicity occurred, and it takes longer than 14 days for the event to resolve to  $\leq$  grade 1, then the participant will be taken off treatment and will remain on study only for survival and other outcomes.

If the toxicity takes less than 14 days to resolve to  $\leq$  grade 1, then ivosidenib can be restarted at 250mg daily dosing upon resolution. If the attributable toxicity recurs at  $\geq$  grade 3 (or grade 4 bilirubinemia in those with known Gilbert’s disease – see above section 6.3) during the course of the study, then the participant will come off treatment and will remain on study only for survival and other outcomes. If the toxicity recurrence (to  $\geq$  grade 3) happens during the first cycle of dosing, then the event will be a DLT.

---

CONFIDENTIAL

This document is confidential. Do not disclose or use except as authorized.

### 6.3.2 500 mg dosing

If the participant was at the 500mg daily dosing level when the toxicity occurred, and the toxicity resolves to  $\leq$  grade 1 *after* 14 days, but *before* 28 days (total) have elapsed, then dosing with ivosidenib can resume at the reduced dose of 250 mg daily. If the attributable toxicity recurs at  $\geq$  grade 3 (or grade 4 bilirubinemia in those with known Gilbert's disease – see above section 6.3) during the course of the study, then the participant will come off treatment and will remain on study only for survival and other outcomes.

If the participant was at the 500mg daily dosing level when the toxicity occurred, and it takes *less than* 14 days for the event to resolve to  $\leq$  grade 1, then dosing with ivosidenib can resume at 500mg daily. If the toxicity recurs at  $\geq$  grade 3 (or grade 4 bilirubinemia in those with known Gilbert's disease – see above section 6.3), then dosing will again be held. (This will be a DLT if it occurs during cycle 1). If the toxicity again resolves to  $\leq$  grade 1 within 28 days, then dosing with ivosidenib can resume at the reduced dose of 250mg daily. If the toxicity recurs yet again at  $\geq$  grade 3 (or grade 4 bilirubinemia in those with known Gilbert's disease – see above section 6.3), then the participant will come off treatment and will remain on study only for survival and other outcomes.

A participant who starts at 500mg daily dosing and is subsequently reduced to 250mg daily dosing due to toxicity can potentially increase back up to 500mg daily dosing if subsequent evaluation of the observed toxicity indicates no relation to study drug. Any such re-escalation must have the approval of the principal investigator, [name].

### 6.4 Concurrent Use of CYP3A4 Inhibitors, CYP3A Inducers, and CYP3A Substrates

Dose adjustment of ivosidenib will be necessary when strong CYP3A4 inhibitors (listed in Appendix E) are initiated or used concurrently, given that concomitant administration with strong CYP3A4 inhibitors is predicted to increase ivosidenib steady-state C max by up to 52% and AUC by up to 90%. For patients at an ivosidenib dose of 500mg daily, concomitant use of strong CYP3A4 inhibitors, the ivosidenib dose will be reduced to 250mg daily, with close monitoring for any toxicity or QT interval prolongation.

The concomitant use of CYP3A inducers (listed in Appendix E) should be avoided. As for concomitant use of CYP3A substrates, this should be avoided when possible, but when this is medically necessary, very close monitoring for toxicity is needed. As an example, tacrolimus and sirolimus are both common immunosuppressive medications, and CYP3A substrates, that post-transplant participants may be taking. Both of these agents will be monitored closely in terms of trough levels, with levels will be doses closely followed and adjusted.

### 6.5 QT Prolongation

Subjects may be at increased risk for the development of QT prolongation when treated with ivosidenib in combination with fluoroquinolones, azole antifungal agents, or serotonin (5-HT3) antagonists. Investigators must be vigilant and attempt to avoid administering concomitant medications associated with QT prolongation whenever possible, and if no other therapeutic options are available, monitor subjects receiving study treatment with the combination of these drugs. They should evaluate ECG and electrolytes (including potassium, magnesium, and calcium) at least weekly for the first cycle of therapy. Vigilance is particularly important in

CONFIDENTIAL

This document is confidential. Do not disclose or use except as authorized.

subjects presenting with nausea, vomiting, or diarrhea. Systemic administration of a moderate or strong CYP3A4 inhibitor requires careful monitoring of QTcF.

Participants who experience QTcF prolongation to  $> 480$  msec (Grade  $\geq 2$ ) while treated with ivosidenib should be promptly evaluated for causality of the QTc prolongation and managed according to the following guidelines:

- Levels of electrolytes (potassium, calcium, and magnesium) should be checked and supplementation given to correct any values outside the normal range.
- Concomitant therapies should be reviewed and adjusted as appropriate for medication with known QT prolonging effects.
- ECGs should be conducted at least weekly for 2 weeks following QTcF reduction  $\leq 480$  msec.

If no other cause is identified and the investigator believes it is appropriate, particularly if QTc remains elevated (after above measures have been implemented, or as determined by the investigator), ivosidenib dosing may be interrupted. An ECG should be rechecked in approximately 1 week after the QTcF prolongation was first observed or more frequently as clinically indicated.

If QTc has recovered or improved and the investigator believes it is safe to do so, re-challenge with ivosidenib should be considered if held.

If Grade 2 (QTcF  $> 480$  and  $\leq 500$  msec), the dose of ivosidenib may be reduced without interruption of dosing. The ivosidenib dose may be re-escalated to the prior dose in  $\geq 14$  days after QT prolongation has decreased to  $\leq$  Grade 1.

If Grade 3 (QTcF  $> 500$  msec), when QTc prolongation is first observed, hospitalization for continuous cardiac monitoring and evaluation by a cardiologist should both be considered. Dosing with ivosidenib will be interrupted. If QTc returns to within 30 ms of baseline or  $< 450$  msec within 14 days, treatment may be resumed at a reduced dose. The ivosidenib dose cannot be re-escalated following dose reduction for Grade 3 QTcF prolongation unless the prolongation was associated with an electrolyte abnormality or concomitant medication.

If Grade 4 (QTcF  $> 500$  msec or  $> 60$  msec change from baseline with torsade de pointes or polymorphic ventricular tachycardia or signs/symptoms of serious arrhythmia), subjects should be admitted to hospital when QTc prolongation is first observed for continuous cardiac monitoring and be discharged only after review by a cardiologist. Dosing with ivosidenib should be permanently discontinued. If, in the dose-escalation cohorts, this discontinuation occurs during the first cycle of treatment, the participant can be replaced, as this would impact DLT assessment.

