**Treatment may not begin without confirmation from the Coordinating Center that the participant has been registered.**

### **5. TREATMENT PLAN**

#### **5.1 Treatment Regimen**

Ivosidenib will be administered orally every day for 28 consecutive days, defined as a treatment cycle. Appropriate dose modifications are described in Section 6. Reported adverse events and potential risks are described in Section 7. No investigational or commercial agents or therapies other than those described below may be administered with the intent to treat the participant's myeloid malignancy.

---

CONFIDENTIAL

This document is confidential. Do not disclose or use except as authorized.

The starting dose of ivosidenib (AG-120) will be 500mg orally daily. After 3 (or 6) participants are treated at 500mg daily, if this dose is tolerated, then an additional 10 participants will be treated at 500mg daily. If the 500mg daily dose is NOT tolerated in the initial cohort of participants, then the dose will be decreased to 250mg daily. If 250mg daily is tolerated, then an additional 10 participants will be treated at 250mg daily. The only doses studied will be 500mg daily and 250mg daily (the latter, if necessary).

The first cohort will consist of three participants. After the third participant is enrolled to the cohort, enrollment will be put on hold until all three participants have completed the first 28-day cycle. The period for dose-limiting toxicity (DLT) evaluation is the first 28-day cycle. Individual participants must receive at least 50% of the dosing to be DLT evaluable for that cohort. If this criteria is not met, the patient in that dose-escalation cohort may be replaced.

If one of three participants in a cohort experiences a DLT, then an additional 3 participants will be observed at that dose. The recommended phase 2 dose (RP2D) is defined as the highest dose level at which 0 or 1 of six participants experiences a dose-limiting toxicity.

Dose Escalation Schedule	
Dose Level	Dose of Ivosidenib
Level 1	250mg daily
Level 2 – Starting Dose	500mg daily

Once the RP2D is defined, an additional 10 participants will be enrolled at that dose.

If 250mg daily dosing is not tolerated, then the study will end without expansion.

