### **6.1 Acute GVHD**

As mentioned previously, acute GVHD prior to study entry must be clinically stable and requiring  $\leq 0.5$  mg/kg/day of prednisone. For patients who initiate therapy and develop new onset acute GVHD:

- Therapy with topical / local agents such as corticosteroid / tacrolimus cream, oral non-absorbable steroids, ursodiol, etc. are allowed to be used and ivosidenib will continue. Discussion with the Principal Investigator is encouraged.

---

CONFIDENTIAL

This document is confidential. Do not disclose or use except as authorized.

- Systemic therapy  $\leq 0.5$  mg/kg/day of prednisone is allowed to be used with continuation of ivosidenib – i.e. starting 20 mg / day for presumed upper GI GVHD. In no way is this study advocating for the use of a specific dose of steroids for initial therapy of acute GVHD, and treatment of such should not be compromised to continue ivosidenib.
- If requiring systemic steroids  $> 0.5$  mg/kg/day of prednisone, ivosidenib will be held and initial therapy for acute GVHD initiated. If within the next 28 days, the participant is able to improve and be on a stable dose of steroids which is  $\leq 0.5$  mg/kg/day of prednisone (or equivalent), ivosidenib may be restarted at the original dose.
- Participants are forbidden from receiving any “investigational” agents for the treatment of acute GVHD. Discussion with the overall PI is encouraged to define “investigational.” Patients are allowed to participate on clinical trials investigating initial therapy for acute GVHD – i.e. using agents with steroids or agents alone which are not “investigational.”
- If acute GVHD occurs in the dose-escalation cohorts, and this occurs during the first cycle of treatment and patient has taken  $< 14$  days of drug, the participant may be replaced, as DLT evaluation would be impacted.
- Any initiation of systemic therapy beyond steroids for steroid-refractory acute GVHD will result in the participant stopping ivosidenib. Systemic therapy beyond steroids for participants with *steroid-dependent* acute GVHD is allowed and will not result in participant stopping ivosidenib. Discussion with the PI is encouraged.
- For flares of acute GVHD, participants are allowed to increase systemic steroid dose, however, if exceeding 0.5 mg/kg/day of prednisone or equivalent, ivosidenib will be held and the patient will have 28 days to restart if symptoms and steroid requirement guidelines can be met.

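### Sections 5.1 and 6.5 (and, less so, 6.1) allow a participant with a cycle 1 DLT to be replaced, so a DLT can leave the at-most-1-in-6 count that sets the RP2D

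*Combined protocol and SAP*

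**What the plan says.** A dose becomes the RP2D when no more than one of six evaluable participants has a DLT in the 28-day first cycle (Sections 5.1, 5.4 and 13).

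**What counts as a DLT.** Section 5.4: "Non-hematologic DLTs will be defined as any drug-related grade 3 or greater event". The only exception is brief, treatable grade 3 nausea, vomiting or diarrhea. A grade 4 neutropenia or thrombocytopenia related to drug counts if, among other routes, it "has not resolved to grade 1 or less within 14 days of holding ivosidenib". Non-hematologic toxicity of grade 2 or higher also counts if the participant finds it intolerable or it "renders the participant unable to take 75% of the assigned doses". Section 6.3 says of related grade 3 or higher toxicity: "If it is during the first cycle (28 days) of dosing, the toxicity will be considered to be a DLT". Section 6.7 does the same for prolonged grade 4 cytopenias. None of these sets a minimum number of doses.

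**Who may be replaced.**
- Section 5.1: "Individual participants must receive at least 50% of the dosing to be DLT evaluable for that cohort", followed by "If this criteria is not met, the patient in that dose-escalation cohort may be replaced".
- Section 6.5, on permanent discontinuation for grade 4 QT prolongation: if "this discontinuation occurs during the first cycle of treatment, the participant can be replaced, as this would impact DLT assessment".
- Section 6.1, on acute GVHD in cycle 1 with fewer than 14 days of drug: "the participant may be replaced, as DLT evaluation would be impacted".
- Section 13: early drop-outs and deaths are unevaluable only if no DLT had occurred and the reason was unrelated to therapy. Only participants unevaluable for DLT may be replaced. The 50% rule does not appear.

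**The concern.** A minimum-exposure rule exists because someone who took little drug and had no DLT tells us little about the dose. Someone who has already had a DLT has given the answer, however few doses were taken. The replacement sentences in 5.1, 6.5 and 6.1 do not make that distinction, and no passage says which section prevails.

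Participants who stop early because of toxicity are the ones most likely to fall under these sentences. Their removal is therefore informative and lowers the counted DLT rate. The RP2D also fixes the dose for the 10-participant expansion and for the planned phase II study, so a miscounted cohort carries forward.

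**Working it through.** **1. The plan's own figure.** Section 13 gives 6 to 22 evaluable patients. Minimum: two or more DLTs in the first three at each level, 3 + 3 = 6. Maximum: 6 + 6 + 10 = 22. Both reproduce. The range counts evaluable patients, so replaced participants fall outside it and it does not cap replacement.

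**2. Section 5.1 against the 75% limb of 5.4.** Taking dosing as the number of daily doses, 50% of 28 is 14 and 75% is 21. For non-hematologic toxicity of grade 2 or higher that prevents dosing:

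| Doses taken | Under 5.4 | Under 5.1 |
|---|---|---|
| 14 to 20 | DLT | evaluable, counted |
| 0 to 13 | DLT | unevaluable, replaceable |

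The participant who lost more dosing to toxicity is the one who can leave the count.

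The overlap is bounded. Drug stopped from day *d* leaves *d* − 1 doses: day 14 leaves 13/28 (46%), day 15 leaves 14/28 (50%). A hold of *L* days inside the cycle leaves 28 − *L*: 13 days leaves 15/28 (54%), 14 days leaves 14/28 (50%), 15 days leaves 13/28 (46%). Apart from other missed doses, the conflict needs drug stopped, or held for more than 14 days, from day 14 or earlier.

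**3. Section 5.1 against the hematologic limb (5.4, 6.7).** For a hold to pass 14 days inside a 28-day cycle it must start by day 14 (14 hold days then end on day 27). That leaves at most 13/28 doses (46%). So nearly every DLT of this type that completes within cycle 1 also fails the 50% rule.

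**4. Section 6.5 against 5.4 and 13.** A drug-related grade 4 QT event is a grade 3 or higher drug-related event and is not excepted, so it is a DLT. Section 6.5 allows replacement without asking about attribution. Section 6.3 excludes QT by its title and 6.7 is hematologic, so neither is in conflict with 6.5.

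**5. Section 6.1.** This is the weakest limb. Acute GVHD is a DLT only if it is judged drug-related and grade 3 or higher, or if it falls under the intolerable/75% limb of 5.4, which does not say whether drug-relatedness is required.

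**6. Effect on one cohort.** Two DLTs in six means de-escalation, or discontinuing the trial at 250 mg. Replace one of the two with a DLT-free participant and the count is 1/6: the dose is the RP2D although 2 of 7 treated participants had a DLT.

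**7. Illustrative size.** Let *p* be the true DLT rate and *f* the share of DLTs replaced. Both are assumptions.

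- With P0 = (1 − p)³ and P1 = 3p(1 − p)², the chance of accepting the dose is P0(P0 + P1) + P1·P0.
- If each DLT is replaced with chance *f* and the place refilled, the counted rate is p(1 − f)/(1 − pf).

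Example, p = 0.40 and f = 0.25: counted rate = 0.30/0.90 = 0.333. Then P0 = 0.296, P1 = 0.444, and acceptance = 0.296 × 0.741 + 0.444 × 0.296 = 0.351. A simulation gave 0.352.

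| True DLT rate p | f = 0 | f = 10% | f = 25% | f = 50% |
|---|---|---|---|---|
| 0.10 | 0.886 | 0.903 | 0.928 | 0.964 |
| 0.20 | 0.655 | 0.695 | 0.758 | 0.863 |
| 0.30 | 0.420 | 0.468 | 0.550 | 0.713 |
| 0.40 | 0.233 | 0.274 | 0.351 | 0.534 |
| 0.50 | 0.109 | 0.136 | 0.191 | 0.351 |

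**The case against.** The best defense is that Section 13 governs the RP2D and already protects the count. It restricts replacement to unevaluable participants and treats a drop-out or death as unevaluable only when no DLT had occurred. The replacement sentences in 5.1, 6.1 and 6.5 are permissive, while the DLT labels in 5.4, 6.3 and 6.7 are mandatory. Read together, a DLT counts and replacement is for everyone else. That is probably what was intended, but the text does not secure it. The sentence in 5.1 on who is evaluable is a requirement, not a permission. It assigns the very status (unevaluable for DLT) that Section 13 makes replaceable. Section 13 never mentions the 50% rule and claims no precedence.

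Several narrower points stand:
- Section 6.5 has a legitimate use, since a grade 4 QT event judged unrelated is not a DLT. Section 7.1.1 puts prolonged QT of any grade at 1–10%, so this route will seldom be used. Section 5.1 is the wider gap.
- Section 6.7 can be read as requiring only that the event begin in cycle 1. Holds from day 15 on would then also give DLTs, and with at least 14 doses taken those remain evaluable.
- All treated patients stay in the toxicity evaluation, and the proportion replaced is reported. That makes a dropped DLT visible afterwards but does not restore it to the RP2D count.
- Registration is central, which makes divergent counting between sites less likely. It does not tell the person counting which section to apply.
- Nothing in the documents supports a particular *f*, and at low *p* the effect is small.

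**Conclusion.** The concern holds. Section 5.1 conflicts with 5.4, 6.3, 6.7 and 13; Section 6.5 conflicts with 5.4 and 13 for drug-related events; Section 6.1 adds a minor gap. Applied as written, 5.1 or 6.5 allows a DLT to be dropped from the primary-endpoint count, and the resulting error can only favor accepting the dose. One such replacement is enough to reverse a cohort decision.

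The probabilities in the table rest on assumed *p* and *f*, independent participants, and the same chance of replacement for every DLT. They show direction and possible scale, not an expected bias. The contradiction and the 2/6 to 1/6 reversal rest on the text alone. Because the conflict lies in the rule that sets the primary endpoint, it must be fixed.

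**What to change.** Adopt one evaluability definition and repeat it, or refer to it, in Sections 5.1, 6.1, 6.5 and 13:

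- A participant with a cycle 1 DLT under Section 5.4 is always DLT-evaluable, whatever number of doses was taken, and is never replaced.
- The 50% rule applies only to participants without a DLT. Add it to Section 13 so that it matches 5.1.
- The replacement sentences in 6.5 and 6.1 apply only to events that do not meet 5.4.
- State which section governs evaluability and replacement.
- State whether the intolerable/75% limb of 5.4 requires the toxicity to be drug-related.

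This changes counting only, not dosing or clinical management. The cost is a wording amendment: no additional patients, possibly fewer replacements, and the 6 to 22 evaluable range is unchanged.
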